2. SYNOPSIS

Study Phase:	4
Financial Disclosure Information for U.S. FDA Submission to be Obtained?	Yes X No
Test Article(s) / Products:	Collagenase SANTYL® Ointment Hydrogel (SoloSite®)
Study Dosage / Usage:	Daily application directly to the ulcer bed, approximately 2-5 mm thick
Active Ingredients:	Collagenase enzymes derived from C. histolyticum, 250 collagenase units per gram of white petrolatum USP
Route of Administration:	Topical
Objective(s):	The primary objective of this study is to compare Collagenase SANTYL® Ointment versus hydrogel in the proportion of ulcers achieving complete debridement following 6 weeks of treatment.
	The secondary objectives are to compare, between groups,
	 The time in days to complete debridement;
	 The percentage reduction in the percentage of non- viable tissue over the 6-week treatment period and at each assessment visit;
	 The percentage reduction in wound area over the 6- week treatment period and at each assessment visit;
	 Change in wound status as measured by the Pressure Ulcer Scale for Healing (PUSH) and Wound Bed Score (WBS) tools following 6 weeks of treatment.
	The exploratory objective of this study is to determine if there is a difference in resource utilization between the two treatment groups.
Study Population:	Adults aged 18 years and older with a pressure ulcer between 1.0 and 64.0 cm ² in area (inclusive) and at least 85% necrotic, non-viable tissue

This document contains confidential information, which is the property of Smith & Nephew, Inc. Do not copy, disclose, or circulate without written authorization from the appropriate Smith & Nephew personnel CONFIDENTIAL DOCUMENT

Structure:	X Parallel Group	Duration of Treatment:	Up to 6 weeks
		Duration of Assessment:	Up to 8 weeks
	Crossover	Number of Treatments:	N/A
		Number of Sequences:	N/A
		Number of Periods:	N/A
		Duration of Periods:	N/A
		Washout Between Periods:	N/A
	Other	N/A	
		Duration of Treatment:	N/A
Multi-Center:	Yes Nu	mber of Centers: 1	
	X No		
Blinding:	None		
	X Observer-Blind		
	Subject-Blind		
	Double-Blind		
Randomization:	X Yes Group As	ssignment Ratio: 1:1	
	No		
Concurrent	No Treatment		
Control:	X Standard Care	Specify: Hydrogel (SoloSite	e®)
	Placebo	Specify: N/A	
	Active	Specify: N/A	
	Other	Specify: N/A	
Estimated Total Sa	1	imately 32 subjects will be rando complete the study	omized to ensure at
Statistical Rational	le Provided: X Ye	S	
	No		
Variable(s): PR	IMARY: Pro	portion of ulcers with complete	debridement
CPT-5.8	Protoc	ol p. 5 of 52	

SECONDARY:

Time in days to complete debridement

Percentage reduction in non-viable tissue

Percentage reduction in ulcer area

PUSH score WBS score

EXPLORATORY:

N/A

SAFETY:

Adverse events

PK:

N/A

Refer to Section 10 for Statistical Design.

Adverse Events:

X Both volunteered and elicited

Other: N/A

3.3 LIST OF ABBREVIATIONS AND DEFINITIONS OF TERMS

Abbreviation	Definition
ABI	Ankle Brachial Index
ADR	Adverse Drug Reactions
AE	Adverse Event(s)
CRF	Case Report Form
FDA	Food and Drug Administration
GCP	Good Clinical Practice
HbAlc	Hemoglobin A1c
IRB	Institutional Review Board
FFF	Intent-to-Treat
LOCF	Last Observation Carried Forward
Norn	Sample Size
NA or N/A	Not Applicable
PP	Per Protocol
PUSH	Pressure Ulcer Scale for Healing
SAE	Serious Adverse Event(s)
SAP	Statistical Analysis Plan
SAS	Statistical Analysis Software, SAS® Institute, Cary, NC
UPT	Urine Pregnancy Test
WBS	Wound Bed Score

4. INTRODUCTION

4.1 BACKGROUND

Pressure ulcers are localized injuries to the skin and underlying tissues, usually over a bony prominence, as a result of pressure and/or shear (1). The proximate causes may be tissue ischemia resulting from restriction of blood supply through the capillaries or alternatively cellular distortion and damage. The effect of stress and strain on deeper tissues must also be considered (2). Factors that may contribute to the breakdown of tissue include moisture, friction, and irritants as well as intrinsic factors such as age, tissue perfusion, nutrition, smoking, diabetes, and steroid treatment, to name just a few (3). Aside from the impact pressure ulcers have on patient health and quality of life, pressure ulcers represent a significant financial cost, not only for institutions and facilities, but also to patients and their families.

Treatment of pressure ulcers is generally aimed at elimination of the cause, i.e., pressure redistribution via repositioning strategies and support structures in conjunction with wound bed preparation consisting of infection control, moisture balance, and debridement (3). Debridement is of particular importance in wound bed preparation as the presence of necrotic tissue in the wound bed represents a burden of senescent cells, dysfunctional extracellular matrix, along with an inflamed proteolytic environment that must be overcome in order for healing to proceed (4,5). Debridement can be accomplished by various means including sharp surgical methods, mechanical (e.g., wet-to-dry gauze), biological (maggots), and enzymatic (collagenase). While sharp surgical debridement is generally acknowledged to be the "gold standard" (6), other methodologies are necessarily employed in situations where there may be a risk of excessive bleeding or where the use of surgical instruments is outside the scope of practice of the wound care practitioners at, for example, a long-term care facility (6,7).

Enzymatic debridement with collagenase has previously been shown to be an effective means of wound bed preparation when used without accompanying sharp debridement for pressure ulcers (7), and for diabetic foot ulcers (8), although additional benefits may be possible if used in

conjunction with sharp debridement (9). In the long-term care setting, debridement with collagenase resulted in more patients achieving complete debridement, more rapidly than when a hydrogel was used (7). The goal of the present study is to confirm the results of this earlier trial, demonstrating superior debridement outcomes for pressure ulcers of patients in long-term care as compared to ulcers managed with a hydrogel.

A summary of known and potential risks and benefits to humans associated with the use of collagenase SANTYL. To ointment can be found in the Investigator's Brochure.

4.2 RATIONALE

Reproducibility is a cornerstone of the scientific method. Indeed, Popper has stated that, "nonreproducible single occurrences are of no significance to science" (10). It is commonly accepted that reproducibility is a necessary condition for the establishment of a scientific fact. According to the National Institute of Standards and Technology, replication of an experiment should include the following elements: the same experimental tools, the same observer, the same measuring instrument used under the same conditions, the same location, repetition over a short period of time, and the same objectives (11). From a practical standpoint it is not generally possible to meet all of these criteria, nevertheless, the design of the present study seeks to replicate as closely as possible the design of a prior study comparing enzymatic debridement with collagenase to passive treatment with a hydrogel. To this end, the study design (i.e., size, number of visits, parallel group, choice of comparator), setting (long-term care facility), inclusion/exclusion criteria, treatment regimen (daily application, no concomitant sharp debridement) endpoints, and objectives are identical to the previous study. The measurement tools are also the same including the PUSH (12) and WBS (13) scales. One of the two observers assessing the ulcer photographs will be the same, although one will be different. However a mechanism to establish consensus in cases of disagreement should mitigate the risk of subjective bias having an important influence on the results. Finally, the objectives of this study exactly match those of the previous trial.

5. OBJECTIVE

The primary objective of this study is to compare Collagenase SANTYL® Ointment versus hydrogel in the proportion of ulcers achieving complete debridement following 6 weeks of treatment.

The secondary objectives are to compare, between groups, the time in days to complete debridement; the percentage reduction in the percentage of non-viable tissue over the 6-week treatment period and at each assessment visit; the percentage reduction in wound area over the 6-week treatment period and at each assessment visit; change in wound status as measured by the PUSH and WBS tools following 6 weeks of treatment.

The exploratory objective of this study is to determine if there is a difference in resource utilization between the two treatment groups.

6. TEST ARTICLES

6.1 IDENTIFICATION

Test Article: Collagenase SANTYL® Ointment - Collagenase enzymes derived from

C. histolyticum, 250 collagenase units per gram of white petrolatum USP.

Control Article: SoloSite® hydrogel

6.2 USAGE

Following normal saline irrigation, SANTYL or SoloSite (depending on treatment assignment) will be applied once daily. SANTYL will be applied directly to the entire wound bed, approximately 2 mm thick (thickness of a nickel). SoloSite will be applied directly to the entire wound bed, approximately 5 mm thick. For both treatment groups, the wound will then be covered with a semi-occlusive dressing (e.g., COVRSITETM). Should the dressing integrity be compromised due to fecal or urinary incontinence, or through inadvertent removal, additional application and dressing should be applied.

6.3 PACKAGING AND LABELING

Packaging and labeling will be prepared to meet regulatory requirements.

The labels on the test article contain the following information:

Study number: 017-101-09-036

Tube number

Subject Number

Place for the Subject Initials

"MUST be Stored at Room Temperature"

Exclusively for Clinical Evaluation Only

Smith & Nephew, Inc., Fort Worth, TX

6.4 TEST ARTICLE ACCOUNTABILITY PROCEDURES

When a delivery of test article is received at the investigational site, the Investigator, or a member of his/her staff specifically authorized and delegated by the Investigator, will check for accurate delivery and acknowledge receipt by signing and dating the required documentation and returning it as instructed. A copy of this documentation will be retained for the Investigator file.

The test article will be stored at room temperature and a temperature log will be maintained by the site.

The receipt, dispensing, and return of test article will be carefully recorded on appropriate accountability forms available for verification by the Sponsor or its designated representative at each monitoring visit. The nursing staff is to be instructed to retain all used and unused test article tubes. Used test article must not be discarded or destroyed by site staff but will be retained for study monitor verification.

7. SUBJECTS

7.1 SUBJECT POPULATION

The study population will consist of approximately 32 adult subjects with a pressure ulcer between 1.0 and 64.0 cm² in area (inclusive), and with at least 85% of the surface covered by necrotic, non-viable tissue.

7.2 INCLUSION CRITERIA

Subjects will be considered qualified for enrollment if they meet the following criteria:

- Provide written informed consent, which will consist of reading, signing, and dating the informed consent document after the Investigator, sub-Investigator or other designated study staff member has explained the study procedures, risks, and contact information.
- 2. Eighteen years of age or older, of either sex, and of any race.

- 3. Willing to comply with protocol instructions, including allowing all study assessments.
- 4. Subject is in-patient in a long-term care facility.
- A pressure ulcer present with a surface area ≥ 1.0 cm² and ≤ 64.0 cm² confirmed using the ImageIQ EDCIQ mobile imaging system. Only one qualifying ulcer per subject will be selected for the study (selection based on greatest clinical need, as assessed by the Investigator).
- The target ulcer must present with ≥85% necrotic, nonviable tissue as assessed by at least one independent image reviewer.
- The target ulcer has not been previously treated with hydrogel (SoloSite[®]) or with SANTYL. Prior ulcers at or near the same location may have been treated with these products.
- No current infections requiring treatment with antibiotics (antibiotic use is permitted for the purpose of urinary tract infection prophylaxis, but this must be explicitly stated in the subject's chart).
- Acceptable state of health and nutrition with pre-albumin levels of ≥ 10 mg/dL (0.10 g/L), per the Screening local lab report. This is not required if a pre-albumin test within range has been conducted within the last 30 days.
- A hemoglobin A1c < 7.9% per the Screening local lab report. This is not required if a hemoglobin A1c test within range has been conducted within the last 30 days.

- Have adequate pressure redistribution to the affected area or off-loading if the ulcer is on a lower extremity.
- 12. No known allergies or sensitivities to either test article or the dressings.
- 13. Women of child-bearing potential (those who are not premenarchal, not surgically sterilized [hysterectomy or bilateral oophorectomy], or not post-menopausal), may participate in the study if they meet the following condition:
 - A negative urine pregnancy test at screening

7.3 EXCLUSION CRITERIA

Any one (1) of the following criteria will disqualify a potential Subject from participation in the study. The Medical Monitor may also declare any subject ineligible for a valid medical reason.

- Undergoing therapy with another investigational agent within thirty (30) days of Study Visit 1, or planned participation overlapping with this study.
- Current oral steroid treatment with a daily dose exceeding 5 mg.
- Inability to comply with off-loading.
- If the ulcer is on a lower extremity, inadequate arterial blood flow to the affected limb as evidenced by an ankle brachial index (ABI) <0.85.
- Presence of callus requiring surgical debridement within 3 days of Study Visit 1.
- Target ulcer with exposure of tendon, muscle or bone.
- Medical condition that, in the opinion of the Investigator, would preclude safe subject participation in the study.

7.4 SCREENING LOG-

The site is required to document all screened subjects (those who have provided informed consent) initially considered for inclusion in this study. If a subject is excluded from the study, the reasons for exclusion will be documented in the subject's source documents and noted on the Screening Log.

8. STUDY DESIGN

[figure not shown]
8.1 STUDY DESIGN

This is a randomized, controlled, parallel observer-blind group study. Subjects providing informed consent will be screened against the inclusion/exclusion criteria. Subjects who meet all of the inclusion criteria and none of the exclusion criteria will be randomly assigned in an equal allocation ratio (1:1) to either SANTYL or to the hydrogel control according to a pre-determined randomization schedule using a blocking technique. Subject randomization will be stratified by the Subject's wound size at baseline resulting in two possible strata: ≥1.0 and ≤10.0 cm²; and >10.0 and ≤64.0 cm². A blocked design will be used for each individual stratum. In either case, caregivers will apply test article once daily (more often as needed for compromised dressing integrity) for up to 6 weeks.

If the ulcer is closed and completely re-epithelialized prior to the end of the 6 week treatment period in either group, the subject will complete Study Visit 7 (Exit) and will be dismissed from the study.

At each weekly visit, the target ulcer will be photographed and area measured using the ImageIQ EDCIQ mobile imaging system. At Study Visit 1 and at Study Visit 7, the ulcer will be assessed using the PUSH and WBS tools. In addition, resource utilization information will be collected at each study visit as described in Section 9.5.

Figure 8.1-1: Study Flow Chart

8.2 METHODS USED TO MINIMIZE BIAS

Due to obvious differences in the physical appearance of the test articles, double-blinding of the study medication is not possible. However, assessments of the ulcer debridement status relating to the presence of non-viable necrotic tissue (primary objective) will be carried out in a blinded fashion by two independent assessors using digital photographs identified only by the subject number and date. Blinded assessment is intended to limit the occurrence of conscious and unconscious bias in the assessment and interpretation of the endpoints. In addition, randomization will be sequential according to a pre-determined, computer-generated randomization schedule. In this way the Investigator will not be able to direct a particular subject to a particular treatment thus preventing treatment allocation bias. Ulcer measurements will be carried out using the ImageIQ EDCIQ mobile imaging system which will minimize subjectivity in theses assessments.

9. STUDY PROCEDURE

For a summary of the required procedures by visit, refer to Table 17-1: *Study Procedures by Visit*.

9.1 VISITS AND EXAMINATIONS

9.1.1 Screening Visit (SCR)

NOTE: Any subject who signs an informed consent, but fails to meet the required entry criteria is considered to be a Screen Failure. Their demographic information must be captured in the Eligibility CRF with the reason for screen failure specified.

Explain the purpose and nature of the study, and have the subject or the subject's legally-authorized representative read, sign, and date the IRB-approved informed consent document. In addition, the informed consent document must be signed and dated by the individual who consents the subject. Provide a photocopy of the signed informed consent document to the subject or subject representative, and place the original signed document in the subject's medical record.

--- Do not proceed until consent has been obtained ---

- Assign a subject ID number (format xx-yyy, where xx=01, the two-digit site number, and yyy=three-digit sequential subject number).
- Obtain demographic information and medical history, including information on all concomitant medications.
- Photograph the target ulcer using the ImageIQ EDCIQ mobile imaging system (refer to Section 9.4.1).
 - Target ulcer area must be between 1.0 cm² and 64.0 cm² (inclusive) and have at least 85% of the surface covered with necrotic, nonviable tissue as assessed by at least one independent image reviewer.
- If the ulcer is on a lower extremity, obtain ABI for the target ulcer limb. ABI must not be less than 0.85.

- Screen the subject for protocol inclusion and exclusion criteria. If the subject does not
 meet ALL inclusion criteria or does meet ANY exclusion criterion, the subject must be
 dismissed as a screen failure.
- Obtain a venous blood sample for serum pre-albumin and hemoglobin A1c measurements (send blood to local laboratory for analysis).
 - **Note**: If an HbA1c or pre-albumin test has been conducted within the last 30 days and is recorded in the subject's chart, an additional test is not required.
- 8. Conduct a urine pregnancy test for women of childbearing potential.
- If any adverse events are observed or reported due to study-mandated procedures (e.g., venous blood sample), the events must be reported as instructed in Section 12, Adverse Events.
- 10. Study Visit I should be scheduled within 7 days of the Screening Visit.

9.1.2 Randomization/Study Visit 1

This visit should occur no more than 7 days after the Screening Visit. Any subject who returns but does not qualify at this visit will be a screen failure and will not be randomized. Upon completion of all screening procedures and confirmation that the subject is eligible for the study, the Investigator or designee will randomize the subject using an electronic randomization system (www.sealedenvelope.com) to obtain the treatment assignment.

The day of the week (Monday, Tuesday, etc.) on which this visit occurs will set the weekly visit day for all subsequent assessments/visits (Study Visits 2 through 7) if the subject is randomized. A (± 1) day visit window will be allowed. If an assessment is not made on the original day of the week for Study Visits 2-7, subsequent visits should be scheduled on the original week day. To minimize differences in baseline ulcer size between the two groups, randomized subjects will be stratified by ulcer size determined at this visit [≥ 1.0 and ≤ 10.0 cm²; ≥ 10.0 and ≤ 64.0 cm²]. Once randomized, subjects will be assessed weekly for the duration of the treatment period (SV1 through SV7).

The following procedures will be completed:

- 1. Record any changes in general health and the use of concomitant medications.
- 2. If any adverse events are observed or reported, they must be recorded as instructed in Section 12, *Adverse Events*.
- Review laboratory results from the blood sample and all other inclusion/exclusion
 criteria.
 - If the blood test results qualify and all entry criteria are met, the subject may be randomized.
- Irrigate the wound with normal saline delivered at 4-15 psi using the Irrimax® device.
 (Sharp debridement is NOT allowed.)
- 5. Photograph the target ulcer using the ImageIQ EDCIQ mobile imaging system. The target ulcer area (cm²) and percentage of the target ulcer surface covered with necrotic, nonviable tissue will be determined by two independent reviewers using the ImageIQ EDCIQ mobile imaging system. The target ulcer area and percentage of necrotic, nonviable tissue must be assessed by at least one independent reviewer prior to the subject being randomized.

Note: If the area of the target ulcer is >64.0 cm², the subject must be screen failed and should not be randomized.

- 6. Assess the wound status using both the PUSH and WBS tools.
- 7. Apply the test article to the entire wound bed according to the instructions for use located in the Study Guide, cover with a semi-occlusive dressing (e.g. COVRSITETM). If the wound has depth, saline-moistened gauze may be used to fill at the Investigator's discretion.
- Ensure that all caregivers are instructed as to the treatment requirements for the study
 protocol and that they are instructed in the application of test article and dressing changes.

Ensure adequate supplies (test article and dressings) are dispensed.

- 9. Record the time spent dressing the ulcer at this visit.
- 10. Schedule the assessment, Study Visit 2, in 7 (± 1) days.

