9.4.2 Percentage of Necrotic Tissue and "Complete Debridement"

All wound photographs will be reviewed in a blinded fashion, identified only by subject number, initials, and date of assessment by two independent reviewers. The reviewers will complete an assessment form providing the percentage of the ulcer covered by non-viable, neerotic tissue as measured using the ImageIQ EDCIQ mobile imaging system. In any case where one reviewer selects 0% or "complete debridement", and the second reviewer does not, the photograph will be re-reviewed at a consensus meeting.

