An initial linear regression model will contain covariates for treatment, baseline (defined as Study Visit 1) ulcer area, baseline percentage of nonviable tissue, and duration of ulcer. A forward selection procedure will be used for the addition of other baseline covariates with an F-value to attain a significance level of 0.1. Further baseline covariates to be assessed as part of this procedure include: subject age, baseline (maximum) ulcer depth, baseline PUSH and WBS scores. The resulting primary analysis presented will correspond to the final model from the forward selection procedure. The results for the initial model will also be presented. For each of the effects in the initial and final model, the p-value, parameter estimate and corresponding 95% confidence interval will be presented. Secondary subgroup analyses may be conducted as a result of the covariate analyses. Additionally, treatment will be fitted on its own in a further linear regression model. The potential for interactions will be examined by fitting the required interaction terms in addition to those effects in the final linear regression model from the forward selection procedure. In each case if the residuals are not normally distributed then non-parametric bootstrapping will be applied. If the nonparametric bootstrap estimates of the confidence intervals for the difference in mean percentage reduction in area between treatments

differ considerably to the standard model estimates, then the nonparametric bootstrap estimates will be used.

The percentage reduction in wound area over the 6-week treatment period will be summarized by treatment separately by the covariates used in the final model.

In addition, a two-sample t-test will be used to test for a difference between treatments in the mean percentage reduction in wound area between Visit 1 and Visit 2. The test will be repeated for comparisons between Visit 1 and Visits 3, 4, 5 and 6 individually. In each case, if normality assumptions do not hold, a Wilcoxon Rank Sum test will be used.

The wound area, reduction in wound area and percentage reduction in wound area at each study visit will be summarized by treatment separately by baseline wound area strata and overall.

The reduction in percentage non-viable necrotic tissue over the 6-week treatment period and at each assessment visit

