For purposes of the analysis, the assessment of percentage non-viable necrotic tissue will be assessed from photographs by two independent reviewers. The following analysis uses the mean of the two percentage non-viable tissue assessments conducted by the independent reviewers for each visit. In the event of disagreement between the two reviewers, the percentage non-viable necrotic tissue used in the following analysis will be the mean of the individual assessments of non-viable necrotic tissue after any consensus meetings have been conducted.

The reduction in the percentage non-viable necrotic tissue will be derived as:

Percentage non-viable necrotic tissue at Study Visit 1 – Percentage non-viable necrotic tissue at Study Visit 7

In cases where a photograph is not taken, the Last Observation Carried Forward (LOCF) method will be used. Sensitivity analyses will be conducted as detailed in the following sections.

The linear regression analysis described in the previous section to test for a difference between treatments in the percentage reduction in wound area over the 6-week will be repeated for the reduction in percentage of non-viable necrotic tissue over the 6-week treatment period. In addition, the separate analysis conducted to test for a difference in percentage reduction in

wound area between treatments between Visit 1 and Visits 2,3,4,5 and 6 will be repeated for the reduction in percentage of non-viable necrotic tissue at the stated time points.

The reduction in percentage non-viable necrotic tissue over the 6-week treatment period will be summarized by treatment separately by the covariates used in the final model. In addition, the percentage non-viable necrotic tissue and reduction percentage non-viable necrotic tissue at each study visit will be summarized by treatment separately by baseline percentage necrotic tissue [categorized] and overall.

Two separate sensitivity analyses will be performed to ensure that the efficacy findings are not reliant on assumptions made in the analysis, derivations or changes agreed between the blinded review panel. The previous section will be repeated with the following modifications using the Full Analysis Set only:

- The "worst case" value will be used. That is, the highest value of percentage non-viable necrotic tissue recorded by the two independent reviewers at each time point will be used for purposes of analysis.

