11. SAMPLE SIZE JUSTIFICATION

A previous study (7) with a design essentially identical to the present study demonstrated highly significant differences between treatment groups for achievement of complete debridement (85% vs. 29%, P<0.003), reduction in % area of non-viable tissue for each week (P<0.002), and in reduction in wound area (P<0.009). The sample size of this previous trial was 27 subjects, 13 in the SANTYL group, and 14 in the hydrogel group. Based on the reported outcomes in the previous trial, 26 subjects are required to detect a difference in the primary endpoint: the proportion of ulcers achieving complete debridement during the 6-week treatment period. This relates to a Fisher's Exact test assuming 85% vs 29% in the proportion of ulcers achieving complete debridement. To allow for 15% drop-out rate throughout the 6-week treatment period, a total of 32 subjects will be randomized (16 per treatment) in an equal allocation ratio for SANTYL and hydrogel. In the previous studies quoted, the secondary endpoints including reduction in % area of non-viable tissue and reduction in wound area were found to reach significance with similar numbers.

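### The non-viable tissue endpoint is a share of each visit's ulcer surface, so unequal area change between arms can distort it; add non-viable area as a pre-specified sensitivity analysis

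*Combined protocol and SAP*

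**What the plan says.** Sections 9.1.2 to 9.1.4 have the ulcer photographed at every study visit. From each photograph two readers determine the ulcer area in cm² and the dead-tissue share: "percentage of the target ulcer surface covered with necrotic, nonviable tissue will be determined by two independent reviewers". Section 9.4.2 describes the form in the same terms: "The reviewers will complete an assessment form providing the percentage of the ulcer covered by non-viable" tissue. Neither section refers the share back to the baseline area.

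Section 10.3.2 defines the six-week change as "Percentage non-viable necrotic tissue at Study Visit 1 – Percentage non-viable necrotic tissue at Study Visit 7", using the mean of the two readers after any consensus meeting. Section 5 words the objective as "the percentage reduction in the percentage of non-viable tissue over the 6-week treatment period and at each assessment visit", a relative rather than an absolute change. Both forms use the ulcer's current surface as denominator.

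For the analysis, the wound-area regression "will be repeated for the reduction in percentage of non-viable necrotic tissue over the 6-week treatment period". That model is specified as follows: "An initial linear regression model will contain covariates for treatment, baseline (defined as Study Visit 1) ulcer area, baseline percentage of nonviable tissue, and duration" (the last item being how long the ulcer has been present). It therefore adjusts for area at baseline but not at follow-up. Visits 2 to 6 are compared by t-test, or by Wilcoxon test if normality fails. The two sensitivity analyses change only which reader's percentage is used. Wound area is a separate secondary endpoint, and the plan never combines area and percentage.

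**The concern.** A share can change because its numerator changes (dead tissue is removed) or because its denominator does (the ulcer closes or widens). The endpoint is meant to describe debridement, but it responds to both. If the clean part of the bed contracts, the remaining ulcer is smaller and relatively more necrotic. If the ulcer widens into viable tissue, the share falls with nothing removed.

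This affects the comparison between arms only if area change differs between them. Section 11 gives a reason to expect that: the earlier trial, which this one sets out to replicate, reported a difference in wound-area reduction (P<0.009). If the arm that debrides better also contracts faster, the measure works against it. If one arm's ulcers enlarge, the measure flatters that arm. At stake is the interpretation of the six-week and weekly tissue comparisons.

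**Working it through.** **Plan's own figure.** The plan gives no numerical planning assumption for this endpoint. The 26 subjects in section 11 are for the primary endpoint (85% v 29%, Fisher's exact test, two-sided 5%). Enumeration gives 80.9% power at 13 per arm and 74.2% at 12, so 26 is reproduced if 80% power was intended; the power is not stated. That figure is not in question.

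**Formula.** Let p0 be the baseline share (at least 85% by section 7.2), r the fraction of the original dead-tissue area that remains, and a the follow-up area divided by the baseline area. The follow-up share is p0·r/a, so

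planned endpoint = p0 − p0·r/a = p0(1 − r/a).

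The reduction in non-viable area is 1 − r, which does not contain a.

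**No dead tissue removed (r = 1).** The true reduction is 0. The planned endpoint gives:

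| Area change | p0 = 85% | p0 = 100% |
|---|---|---|
| +10% | 85(1 − 1/1.1) = 7.7 points | 9.1 points |
| +20% | 85(1 − 1/1.2) = 14.2 points | 16.7 points |
| +50% | 85(1 − 1/1.5) = 28.3 points | 33.3 points |
| −10% | 85(1 − 1/0.9) = −9.4 points | not possible |

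Shrinkage without removal cannot exceed 1 − p0, which is at most 15% of the area. Growth has no such bound.

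**Hidden difference.** Both ulcers start at 10 cm² and 90%, so 9 cm² is dead.
- A shrinks to 5 cm² with 2.25 cm² dead: share 45%, endpoint 45 points, non-viable area down 75%.
- B stays at 10 cm² with 4.5 cm² dead: share 45%, endpoint 45 points, non-viable area down 50%.

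**Reversed difference.** Same start.
- A shrinks to 5 cm² with 2.5 cm² dead: 90 − 50 = 40 points, non-viable area down 72%.
- B stays at 10 cm² with 4.0 cm² dead: 90 − 40 = 50 points, non-viable area down 56%.

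**Simulated trials.** There were 16 per arm, with baseline share uniform on 85–100%. Remaining dead tissue is a median fraction times a lognormal factor (SD 0.6 on the log scale), capped at 100%. The fraction of viable bed closed is normal with SD 0.2. The test is Wilcoxon at 5%. Medians, closure rates and spreads are all assumptions; the documents give none.

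| Median dead tissue left | Closure of viable bed | Planned share: rejects | Non-viable area: rejects |
|---|---|---|---|
| 35% v 65% | 20% both | 75% | 79% |
| 35% v 65% | 30% v 10% | 54% | 76% |
| 35% v 65% | 50% v 10% | 22% | 77% |
| 50% both | 30% v 10% | 9% | 5% |
| 50% both | 50% v 10% | 27% | 5% |

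Reruns agree within a few points. In the last two rows the rejections mostly favour the slower-closing arm.

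**At six weeks,** with 85% v 29% of ulcers fully clean (median 50% v 60% left in the rest), the choice of test matters. At closure 60% v 20%, Wilcoxon gives 76% for the share v 92% for non-viable area, but it still gives 84% v 91% when closure is 20% in both arms. An unadjusted t-test gives 82% v 89%, and 89% v 89% at equal closure. The distortion is therefore modest at six weeks and falls mainly on partly clean ulcers at earlier visits.

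**The case against.** The strongest objection comes from section 11 itself. The sentence that reports the area difference also reports that the reduction in non-viable tissue separated the arms each week (P<0.002), in 27 subjects. That is the only evidence in the documents on whether this measure conceals an effect, and it points the other way. A reader might infer from the examples above that the planned endpoint will hide or reverse a treatment difference. The documents do not support that. The largest losses need a five-fold difference in closure, and with equal closure the two measures perform almost alike.

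A reader might also infer that non-viable area should replace the planned measure. Two things stand against this. First, section 4.2 makes replication the study's rationale and says that endpoints and objectives match the previous trial; section 5 states the tissue objective in terms of the percentage. Second, non-viable area has the mirror-image weakness: it falls when the whole ulcer shrinks at an unchanged necrotic share. With the same distribution of necrotic share in both arms and proportional shrinkage of 30% v 10%, a simulation has non-viable area rejecting in 20% of trials and the planned measure in 4%; at 50% v 10% it is 76% v 4%. Which measure is apt depends on whether the target is bed composition or necrotic burden.

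Both objections stand against replacement and against a forecast of harm. Neither answers the narrower point: the planned analysis alone cannot show whether a tissue result reflects debridement or change in ulcer size. Analysing wound area separately does not settle this, because the two results are never combined within a subject.

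**Conclusion.** The point holds as an interpretability gap in one secondary endpoint. The dependence on area ratio follows from the definition, and neither the covariates nor the planned sensitivity analyses remove it. Its size in this trial is unknown. Under the assumptions above, power ranges from 75% (equal closure) through 54% (30% v 10%) to 22% (50% v 10%), against 76–79% for non-viable area. False separation with equal removal is 9–27%. These figures illustrate what unequal closure could do and do not predict the result.

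The primary endpoint is unaffected: while an ulcer is open, 0% non-viable is 0% on either measure. Time to complete debridement is likewise unaffected while the ulcer is open, and the sample size is not touched. This is a cheap improvement to the plan, not a fault in its main conclusion.

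**What to change.** Keep the planned percentage-point reduction as the lead tissue measure, in line with the objective and the replication aim. In section 10.3.2 and in the SAP, add one pre-specified sensitivity analysis:

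- For each reader and visit, non-viable area (cm²) = ulcer area × percentage non-viable / 100; average over the two readers; a closed ulcer counts as 0 cm².
- Analyse the percentage reduction in non-viable area from Study Visit 1 with the same regression and visit-by-visit tests.
- State the reading rule in advance: a tissue difference is interpreted as a debridement effect only if the two measures agree in direction. If they disagree, it is reported as confounded with change in ulcer size.

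The cost is one derived variable from two values already recorded for each photograph, plus wording in the protocol section and in the SAP, which section 10 says is to be finalised before database lock. No visits, readings or subjects are added. The analysis also gives closed ulcers a defined value; the plan sets their area to 0 cm² but states no percentage. The downside is one more secondary analysis, on a measure with its own sensitivity to proportional shrinkage, so it complements the percentage and does not replace it.
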